## APPENDIX I

### **Performance Status Criteria**

### ECOG Performance Status Scale

Grade	Descriptions
0	Normal activity. Fully active, able to carry on all pre-disease performance without restriction.
1	Symptoms, but ambulatory. Restricted in physically strenuous activity, but ambulatory and able to carry out work of a light or sedentary nature (e.g., light housework, office work).
2	In bed <50% of the time. Ambulatory and capable of all self-care, but unable to carry out any work activities. Up and about more than 50% of waking hours.
3	In bed >50% of the time. Capable of only limited self-care, confined to bed or chair more than 50% of waking hours.
4	100% bedridden. Completely disabled. Cannot carry on any selfcare. Totally confined to bed or chair.
5	Dead.

### APPENDIX II

#### RESPONSE CRITERIA FOR ACUTE LEUKEMIA

##### **Morphologic leukemia-free state**

Bone marrow < 5% blasts in an aspirate with spicules

No blasts with Auer rods or persistence of extramedullary disease

Absolute neutrophil count < 1000/mcL AND platelets <100,000/mcL

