### **5.3. Study design**

**5.3.1 Definition of complete remission (CR):** An evaluable patient will be classified as having complete remission if they meet the criteria in Appendix II.

**Decision Rule (Simon two-stage design):** The largest CR rate where the proposed treatment regimen would be considered ineffective in this population is 35%. Subsequent studies will be warranted if the CR rate is 50% or higher or the CR rates are similar to historical data but

the disease-free survival and the overall survival are improved in comparison to our institution's historical cohort. The following optimal Simon two stage design uses 44 patients to test the null hypothesis that the true CR rate in the given patient population is at most 35%.

**Stage 1:** Enter 16 evaluable patients. If 5 or fewer patients have a CR in this timeframe, we will consider this early evidence that this treatment regimen is not sufficiently efficacious in this patient population, and the accrual of patients will be stopped. If 6 or more patients have a CR, then accrual will continue in the second stage of this trial.

**Stage 2:** Enter an additional 28 evaluable patients to the trial. If 19 or more patients achievea complete remission, the treatment will be promoted for further consideration. This design has  $\alpha=0.15$  and  $\beta=0.20$ ; the large value of  $\alpha$  is appropriate in an early phase trial. If the probability of CR is 35%, the expected sample size is 30.3 patients, i.e., the probability that the trial will be halted after 16 patients is 48.9%.

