### **Complete remission**

Bone marrow < 5% blasts in an aspirate with spicules  
Absolute neutrophil count > 1000/mcL

Platelets  $\geq$ 100,000/mcL

No residual evidence of extramedullary disease

Morphologic CR - patient independent of transfusions

Cytogenetic CR - cytogenetics normal (in those with previously abnormal cytogenetics)

Molecular CR - molecular studies negative

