### **Complete remission with incomplete hematologic recovery**

Bone marrow < 5% blasts in an aspirate with spicules

No residual evidence of extramedullary disease

Absolute neutrophil count > 1000/mcL or platelets  $\geq$ 100,000/mcL

No residual evidence of extramedullary disease

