### **Relapse**

Relapse following complete remission is defined as reappearance of leukemic blasts in the peripheral blood or the finding of more than 5% blasts in the bone marrow, not attributable to another cause (eg, bone marrow regeneration after consolidation therapy)

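### Appendix II: CR and CRi lack the Auer-rod exclusion that the lesser leukemia-free state carries, and relapse omits extramedullary recurrence although extramedullary disease bars CR

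*Combined protocol and SAP*

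**What the plan says.** Section 5.3.1 ties the primary endpoint to the appendix: "An evaluable patient will be classified as having complete remission if they meet the criteria in Appendix II". The Simon two-stage rule in the same section counts those CRs.

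Appendix II then sets these conditions:

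- **Morphologic leukemia-free state (MLFS):** under 5% blasts, "No blasts with Auer rods or persistence of extramedullary disease", and "Absolute neutrophil count < 1000/mcL AND platelets <100,000/mcL".
- **CR:** "Bone marrow < 5% blasts in an aspirate with spicules", "Absolute neutrophil count > 1000/mcL", platelets of at least 100,000/mcL, and "No residual evidence of extramedullary disease". Auer rods are not mentioned.
- **CRi:** the same marrow and extramedullary conditions (the extramedullary line is printed twice) and "Absolute neutrophil count > 1000/mcL or platelets" of at least 100,000/mcL. Auer rods are not mentioned.
- **Relapse after CR:** "reappearance of leukemic blasts in the peripheral blood or the finding of more than 5% blasts in the bone marrow", unless another cause explains it. Extramedullary disease is not mentioned.

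Auer rods appear nowhere else in the protocol. Sections 1.1 and 5.4.2 name progression-free survival, while Sections 4.0 and 5.3.1 speak of disease-free survival. Neither is given an event definition. The Relapse entry is the only rule in the documents for loss of remission.

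**The concern.** A response scale should not become looser on residual leukemia as the category improves. Here the lowest remission-type category excludes blasts with Auer rods, and the two better ones do not. Because the primary endpoint is scored on these lists, a marrow that the appendix itself does not accept as leukemia-free can be counted as a success.

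The second gap concerns loss of remission. A finding that would have prevented CR does not end it. This matters beyond descriptive survival curves, because Section 5.3.1 offers a second route to further study: a CR rate similar to historical data, with better disease-free and overall survival than the institution's historical cohort. After the recovery marrow, Section 4.0 moves follow-up to remote chart review. Whoever abstracts a charted extramedullary recurrence needs a written rule for it.

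**Working it through.** No figure in the plan is disputed here, so the check applies the lists as written to specific patients.

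**Step 1. Auer rods.** Take a marrow with 3% blasts and vary the other items. ANC and platelets are per mcL, and transfusion independence is assumed where CR is scored.

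| Auer rods | Extramedullary disease | ANC | Platelets | MLFS | CR | CRi |
|---|---|---|---|---|---|---|
| no | none | 500 | 50,000 | yes | no | no |
| yes | none | 500 | 50,000 | **no** | no | no |
| yes | none | 1500 | 50,000 | no | no | **yes** |
| yes | none | 1500 | 150,000 | no | **yes** | yes, as worded |
| no | present | 1500 | 150,000 | no | no | no |

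Rows 1 and 2 differ only in Auer rods, and the rods alone remove the patient from MLFS. Rows 2 and 4 have the same marrow and differ only in blood counts. The patient who was not leukemia-free at low counts is a CR when counts recover. Row 5 shows that the lists do treat extramedullary disease consistently across the three categories, so the Auer-rod condition is the one that drops out.

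**Step 2. Relapse.** Take a patient in CR who develops new soft-tissue disease, with no blasts in the blood and 3% in the marrow.

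- Blood criterion: not met.
- Marrow criterion, above 5%: not met.
- Result: no relapse. The same extramedullary finding at response assessment would have ruled out CR.

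If the Relapse entry supplies the event, one of three things follows:

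- Blood or marrow later meets the rule, and the event is dated late.
- The patient dies first, and the event is again late.
- Neither happens before the end of follow-up, and the event is missed.

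Each of these lengthens the trial's estimated disease-free or progression-free survival.

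**Step 3. Size.** The effect on the CR rate is the share of evaluable patients with under 5% blasts, Auer rods, both counts recovered and no extramedullary disease. The effect on disease-free survival depends on the share of first recurrences that are extramedullary only. The documents give neither share, so neither effect can be computed from them.

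**The case against.** The strongest reply is that both gaps are narrow. The first needs several features together in one patient: under 5% blasts, visible Auer rods, both lineages recovered and no extramedullary disease. In the second, some events are only late, because marrow relapse or death would still count. Appendix II also ends with a citation to published response criteria, so the lists may simply be abbreviated. The narrowness stands and limits the weight of the point. The citation does not settle it: nothing says that the source completes or overrides the lists, and Section 5.3.1 points to the appendix itself.

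It can also be said that no passage makes the Relapse entry the event for progression-free or disease-free survival. That is correct, and the bias is therefore conditional. The documents supply no other definition, however.

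A reader might infer four stronger things that the documents do not support:

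- **That the Auer-rod gap could readily flip the stage 1 decision.** The chance that stage 1 ends on exactly 6 CRs in 16 is only the chance of sitting on the boundary. It would have to be multiplied by the unknown chance that at least one of those six is an Auer-rod case.
- **That CR and CRi must be double counted.** As worded, every CR also meets the CRi count condition. But the category title says recovery is incomplete, and assigning each patient the best category met removes the overlap. CRi is not a named endpoint, and the CR count does not change.
- **That a marrow at exactly 5% is an inconsistency.** CR needs less than 5% and relapse more than 5%, but entry to and loss of remission need not be complementary. A patient in CR whose marrow later shows exactly 5% has simply not relapsed. Moving the relapse cut-off would be a preference and would not alter any CR.
- **That the comparison with the historical cohort is certainly biased in the trial's favor.** The documents do not say how relapse was scored in that cohort. If the same rule was used, both sides share the gap.

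**Conclusion.** Two inconsistencies in Appendix II stand on the text, and both touch endpoints. The Auer-rod omission can let residual leukemia count as CR, the primary endpoint. The relapse omission leaves extramedullary-only recurrences without a date. It overstates the trial's disease-free or progression-free survival if the Relapse entry is the event, and it biases the historical comparison unless the cohort was scored by the same rule.

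The size cannot be calculated from the documents. Few patients are likely to be affected; that is a judgment, not a computed figure. The Simon design's boundaries and error rates are not called into question. The edits should be made because they are specific and cheap and bear on the primary endpoint and on one stated route to further study. The gaps are drafting omissions and do not undermine the design.

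**What to change.** Make two edits in Appendix II:

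1. Under CR and under CRi, add *no blasts with Auer rods*. A patient with under 5% blasts, recovered counts and Auer rods would then not be a CR, and would fall under the existing line that treats patients without CR as treatment failures.
2. Under Relapse, add *or reappearance or new development of extramedullary disease*.

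Apply both to every patient, preferably before responses are adjudicated, so that the choice is not made with outcomes known. State which relapse rule is used for the historical cohort in the disease-free survival comparison.

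Optional tidying in the same amendment:

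- State that CRi excludes patients who meet CR.
- Align the ANC cut-offs. MLFS needs ANC below 1000/mcL, CR and CRi use above 1000/mcL, and Section 4.0 treats 1000 or more as count recovery. As written, ANC of exactly 1000/mcL with platelets under 100,000/mcL falls in none of MLFS, CR or CRi. Rewording CRi as one lineage below threshold but not both would need care, because with a cut-off of 1000 or less that patient would still fit no category.

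The cost is wording only: no new tests, visits or patients. The downside is a CR count that may be slightly lower and slightly more relapse events.

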### **Complete remission**

Bone marrow < 5% blasts in an aspirate with spicules  
Absolute neutrophil count > 1000/mcL

Platelets  $\geq$ 100,000/mcL

No residual evidence of extramedullary disease

Morphologic CR - patient independent of transfusions

Cytogenetic CR - cytogenetics normal (in those with previously abnormal cytogenetics)

Molecular CR - molecular studies negative

### **Complete remission with incomplete hematologic recovery**

Bone marrow < 5% blasts in an aspirate with spicules

No residual evidence of extramedullary disease

Absolute neutrophil count > 1000/mcL or platelets  $\geq$ 100,000/mcL

No residual evidence of extramedullary disease

### **Partial remission**

Decrease of at least 50% in the percentage of blasts to 5 to 25% in the bone marrow

Patients failing to achieve a complete remission are considered treatment failures

### **Relapse**

Relapse following complete remission is defined as reappearance of leukemic blasts in the peripheral blood or the finding of more than 5% blasts in the bone marrow, not attributable to another cause (eg, bone marrow regeneration after consolidation therapy)

## **9. DRUG INFORMATION**

## **Gemtuzumab Ozogamicin**

**Other Names:** Mylotarg

**Classification:** Antibody-drug conjugate

**Mechanism of Action:** Antibody-drug conjugate to CD33 antigen. Binding results in internalization of the antibody-antigen complex. Following internalization, the calicheamicin derivative is released inside the myeloid cell. The calicheamicin derivative binds to DNA resulting in double strand breaks and cell death. Pluripotent stem cells and nonhematopoietic cells are not affected.

**Storage and Stability:** GO is supplied as a sterile, pyrogen-free, unpreserved, white lyophilized powder in amber glass vials. The unopened vials of GO should be stored at 2 - 8° C (refrigerated) and protected from light and should be used within 8 hours of reconstitution. GO is light sensitive and should be reconstituted, prepared, and administered under protection from direct/indirect sunlight and Ultraviolet (UV) light.

**Dose Specifics:** GO will be administered at 3 mg/m^2 (cap at 4.5mg) on day 6. BSA will be calculated based on actual body weight.

**Preparation:** GO is light sensitive and must be protected from direct and indirect sunlight and unshielded fluorescent light during the preparation and administration of the infusion. ALL PREPARATION SHOULD BE DONE IN A BIOLOGIC SAFETY HOOD WITH FLUORESCENT LIGHT OFF. Prior to reconstitution, allow vials to come to room temperature for approximately 5 minutes. Reconstitute the contents of each vial with 5 mL sterile water for injection, USP, using sterile syringes. Gently swirl each vial. The final concentration is 1 mg/mL. Use reconstituted solution immediately or after being refrigerated at 2-8°C for up to 1 hour. Protect reconstituted solution from light. Do not freeze reconstituted solution. Dilute the desired volume of GO into a 50-milliliter

intravenous bag of 0.9% sodium chloride injection or other appropriate volume of 0.9% sodium chloride to make a final GO concentration between 0.075 mg/ml to 0.234 mg/mL. Gently invert the infusion container to mix the diluted solution. Do not shake. Following dilution with 0.9% sodium chloride injection, GO solution should be infused immediately. If not used immediately, store at room temperature (15–25°C; 59–77°F) for up to 6 hours, which includes the 2-hour infusion time and 1-hour, if needed, to allow the refrigerated diluted solution to equilibrate to room temperature. The diluted solution can be refrigerated at 2– 8°C (36–46°F) for up to 12 hours which includes up to 1-hour in the vial post-reconstitution.

**Route of Administration:** GO is administered as a 2 hour IV infusion. A 0.2-micron polyethersulfone filter is required on the IV line. The IV bag must be protected from light using a light-blocking cover during infusion. The infusion line does not need to be protected from light.

**Compatibilities:** No information; infuse via separate line.

**Availability:** Commercially available

**Side Effects:**

**Common** (occurs in more than 10% of people - more than 10 out of 100 people): fever (79%), infection (42%), increased AST (40%), sepsis (32%), bleeding (23%), nausea and vomiting (21%), constipation (21%), mucositis (21%), headache (19%), increased ALT (16%), rash (16%)

**Infrequent** (occurs in 1% to 10% of people - from 1 to 10 out of 100 people): pneumonia (7%), bleeding (7%), hyperbilirubinemia (7%), mucositis (4%), pain (4%), diarrhea (2%), headaches (2%), tachycardia (2%), lung edema (2%)

**Rare** (occurs in <1% of people, mainly identified in post-marketing surveillance):

neutropenic colitis, interstitial pneumonia, hemorrhagic cystitis

**Nursing Implications:** Patients should be premedicated prior to administration of GO with methylprednisolone 1 mg/kg IV, diphenhydramine 50 mg IV or PO and acetaminophen 650 mg PO 30 minutes prior to start of the infusion. Additional doses of acetaminophen and diphenhydramine may be administered every 4 hours after the initial pretreatment dose. Repeat with the same dose of methylprednisolone for any sign of an infusion reaction, such as fever, chills, hypotension, or dyspnea during the infusion or within 4 hours afterwards.

During and after the infusion patients will be monitored with vital signs recorded every 30 minutes during the infusion and for 1 hour after completion of the infusion.

GO should be administered in a setting where appropriate medical support, including life support equipment, is available in case of an unexpected adverse event.

## **Etoposide**

**Other Names:** Toposar

**Classification:** Podophyllotoxin Derivative

**Mechanism of Action:** Etoposide has been shown to delay transit of cells through the S phase and arrest cells in late S or early G2 phase. The drug may inhibit mitochondrial transport at the NADH dehydrogenase level or inhibit uptake of nucleosides into HeLa cells. It is a topoisomerase II inhibitor and appears to cause DNA strand breaks. Etoposide does not inhibit microtubular assembly.

**Storage and Stability:** Unopened vials of etoposide are stable for 24 months at room temperature (25 degrees Celsius). Vials of etoposide are stable at room temperature for 96

hours when diluted to concentrations of 0.2 milligrams/milliliter (mg/mL); stability is 24 hours with concentrations of 0.4 mg/mL at room temperature. The manufacturer does not recommend that etoposide be administered at concentrations greater than 0.4 mg/mL because time to precipitation is highly unpredictable and precipitate formation has been reported to occur earlier than the utility times listed above. Etoposide 20 mg/ml is stable in a plastic syringe for 5 days when stored at room temperature under fluorescent light.

**Dose Specifics:** Patients will receive etoposide 100 mg/m^2 administered intravenously in 500 ml of 0.9% sodium chloride over 2 hours on days 1-5 (for patients who have elevated total bilirubin, AST or reduced creatinine clearance during the etoposide infusion see treatment schema for dose modification of the etoposide). BSA will be calculated based on actual body weight.

**Preparation:** Etoposide Injection must be diluted prior to use with either 5% Dextrose Injection, or 0.9% Sodium Chloride Injection, to give a final concentration of 0.2 to 0.4 mg/mL . If solutions are prepared at concentrations above 0.4 mg/mL, precipitation may occur. Parenteral drug products should be inspected visually for particulate matter and discoloration prior to administration whenever solution and container permit.

**Route of Administration:** Etoposide should be given as a diluted solution via the IV route.

**Compatibilities:** Variable stability (consult detailed reference) in D5W, LR, NS.Y-site administration: Compatible: Allopurinol, amifostine, aztreonam, cladribine, doxorubicin liposome, fludarabine, gemcitabine, granisetron, melphalan, ondansetron, paclitaxel, piperacillin/tazobactam, sargramostim, sodium bicarbonate, teniposide, thiotepa, topotecan, vinorelbine. Incompatible: Cefepime, filgrastim, idarubicin.

**Compatibility when admixed:** Compatible: Carboplatin, cisplatin, cisplatin with cyclophosphamide, cisplatin with floxuridine, cytarabine, cytarabine with daunorubicin, floxuridine, fluorouracil, hydroxyzine, ifosfamide, ifosfamide with carboplatin, ifosfamide

with cisplatin, ondansetron. Variable (consult detailed reference): Cisplatin with mannitol and potassium chloride, doxorubicin with vincristine.

**Availability:** Commercially available

**Side Effects:**

**Common** (occurs in more than 10% of people - more than 10 out of 100 people):  
Alopecia (8% to 66%), ovarian failure (38%), Nausea/vomiting (31% to 43%), anorexia (10% to 13%), diarrhea (1% to 13%), leukopenia (60 to 91%), thrombocytopenia (22% to 41%), anemia (up to 33%), mucositis

**Infrequent** (occurs in 1% to 10% of people - from 1 to 10 out of 100 people):  
Hypotension (1% to 2%), stomatitis (1% to 6%), abdominal pain (up to 2%), hepatic toxicity (up to 3%), peripheral neuropathy (1% to 2%), anaphylactic-like reaction (IV infusion 1% to 2%)

**Rare** (occurs in fewer than 1% of people – fewer than 1 out of 100 people):  
Congestive heart failure, hyperpigmentation, rash, radiation-recall reaction, StevensJohnson Syndrome, pruritus, toxic epidermal necrolysis, cyanosis, optic neuritis, transient blindness, diaphoresis, interstitial pneumonitis, pulmonary fibrosis, metabolic acidosis, thrombophlebitis, extravasation

**Nursing Implications:** For IV use only; may cause severe local tissue damage if extravasation occurs. Do not administer intrathecally; may cause serious and permanent neurologic damage. Should be administered under the supervision of an experienced cancer chemotherapy physician.

**Mitoxantrone**

**Other Names:** Dihydroxyanthracenedione, DHAD

**Classification:** Anthracenedione

**Mechanism of Action:** Analogue of the anthracyclines, mitoxantrone intercalates DNA; binds to nucleic acids and inhibits DNA and RNA synthesis by template disordering and steric obstruction; replication is decreased by binding to DNA topoisomerase II and seems to inhibit the incorporation of uridine into RNA and thymidine into DNA; active throughout entire cell cycle

**Storage and Stability:** Intact vials should be stored between 15 and 25 degrees Celsius (59 and 77 degrees Fahrenheit). DO NOT FREEZE. After penetration of the stopper, store the remaining solution of undiluted mitoxantrone for no longer than 7 days between 15 to 25 degrees Celsius (59 to 77 degrees Fahrenheit) or for no longer than 14 days under refrigeration (2 to 8 degrees Celsius or 36 to 46 degrees Fahrenheit). Mitoxantrone must be further diluted for infusion.

**Dose Specifics:** Patients will receive mitoxantrone 10mg/m^2 administered IVPB in 50ml 0.9% sodium chloride over 15 minutes on days 1-5. (Refer to Treatment Plan of Phase I and II sections). BSA will be calculated based on actual body weight.

**Preparation:** MITOXANTRONE CONCENTRATE MUST BE DILUTED PRIOR TO USE. Dilute the dose with at least 50 milliliters (mL) of 0.9% sodium chloride or 5% dextrose in water. Dilution in volumes greater than 50 mL may be done in 5% dextrose in water, 0.9% sodium chloride, or dextrose 5% with 0.9% sodium chloride. Parenteral drug products should be inspected visually for particulate matter and discoloration prior to administration whenever solution and container permit.

**Route of Administration:** Mitoxantrone should be given as a diluted solution via the IV route.

**Compatibilities:** Stable in D5NS, D5W, NS Y-site administration: Compatible: Allopurinol, amifostine, cladribine, etoposide phosphate, filgrastim, fludarabine, gatifloxacin, gemcitabine, granisetron, linezolid, melphalan, ondansetron, sargramostim, teniposide, thiotepa, vinorelbine. Incompatible: Amphotericin B cholesteryl sulfate complex, aztreonam, cefepime, doxorubicin liposome, paclitaxel, piperacillin/tazobactam, propofol.

**Compatibility when admixed:** Compatible: Cyclophosphamide, cytarabine, fluorouracil, hydrocortisone sodium succinate, potassium chloride. Incompatible: Heparin. Variable (consult detailed reference): Hydrocortisone sodium phosphate.

**Availability:** Commercially available

